## Clinical Evaluation of Kerr SonicFill™ 2 vs 3M ESPE Filtek™ Supreme Ultra Universal Restorative

Principal Investigator:	[name], DMD, MS, PhD
Co-Investigators:	[name], DMD, MS [name], DMD [name], DMD, PhD [name] [name], MPH, PhD [name], DMD, MS
Study Location:	Tufts University School of Dental Medicine [name]
Sponsor:	Kavo Kerr Group
Protocol Version Date:	11/2/2018

Clinical Evaluation of Kerr SonicFillTM 2 vs 3M ESPE FiltekTM Supreme Ultra Universal Restorative PI: [name], DMD, MS, PhD

I) Introduction

A) Aim/Hypothesis/Objective

The primary objective of this study is to evaluate the clinical performance of a sonic-activated, bulk fill composite, SonicFill™ 2, by comparing it to Filtek™ Supreme Ultra in the following categories:

#### Esthetic Properties

- Surface luster
- Staining surface
- Staining margin
- Color match and translucency
- Esthetic anatomical form

#### Functional Properties

- Fracture of material and retention
- Marginal adaptation
- Aproximal anatomical form contact point
- Radiographic examination (when applicable)
- Patient's view

#### **Biological Properties**

- Postoperative (hyper-)sensitivity and tooth vitality
- Recurrence of caries, erosion, abfraction
- Tooth integrity (enamel cracks, tooth fractures)
- Adjacent mucosa

The hypothesis to be tested is that the sonic-activated, bulk fill composite, SonicFill™ 2, will have comparable results to the traditional incremental technique composite, Filtek™ Supreme Ultra, in overall clinical acceptability and in all compared categories

II) Background and Rationale

Marginal leakage appears to be an inherent shortcoming of all dental restorations.  Various techniques have been advocated to enhance the marginal adaptation and reduce the microleakage of composite restorations. Multilayer techniques, in contrast to bulk packing methods, have decreased marginal gap formations. The size reduction of the composite material, the diminution of polymerization shrinkage, and the enlargement of the free surface area in relation to the volume are of great importance in this context.  When the whole margin area is first filled with an increment, fewer contraction gaps at the margins can be expected.

Traditional, incrementally filled dental composite material has been on the market for many years, and has been proven successful for use in posterior restorations. Traditional composite techniques require small amounts (up to 2mm) of composite be placed at a time and then light cured. This process is pain staking and time consuming. Newer products on the market are bulk fill – allowing increments of up to 5mm to be placed before light curing. Many of these products then require a capping material to be placed over them. The newer SonicFill™ 2 system is a sonic-activated, bulk fill composite that allows placement of material up to 5mm without the need for a capping layer. The sonic activated technique allows for easy placement and good adaptation of the restoration. This process also shortens the time necessary to complete a restoration, which benefits both the dental practitioner and the dental patient.

#### Standard of Care at TUSDM clinics

The standard of care in the TUSDM clinics is to place composite following the incremental technique with Filtek™ Supreme Ultra (the resin composite used as a control in this study).

#### III) Research Plan

A) Experimental Design

This study is a randomized, split-mouth, controlled, examiner-blinded clinical evaluation of Class II restorations using a new bulk-fill composite (SonicFill™ 2) and comparing it to 3M ESPE Filtek™ Supreme Ultra resin composite placed in the traditional incremental technique.

B) Sample Size and Statistical Analysis

#### Sample size

A sample size calculation was conducted using nQuery Advisor (version 7.0). The calculation determined that with a sample size of n=35 subjects, all 95% confidence intervals will have a margin of error of no more than 16.6%. Up to 44 subjects will be treated to allow for 20% dropout. Up to 100 will be screened to have 35 qualifying subjects complete the study.

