#### Statistical analysis

Tables of descriptive statistics (counts and percentages for categorical variables, means and standard deviations for continuous variables) will be prepared to summarize the demographic characteristics of the patients, the distribution of restorations and baseline data, and to illustrate the recall and data analysis findings. Because the hypothesis of the study does not involve superiority of one technique over another, and comparable results between SonicFill™ 2 and Filtek™ Supreme Ultra are anticipated, confidence intervals will be used rather than p-values. In particular, for each evaluation category, the percentage of times that SonicFill™ 2 outperforms Filtek™ Supreme Ultra, the percentage of times that Filtek™ Supreme Ultra outperform SonicFill™ 2, and the percentage of times with equal performance will be calculated along with 95% confidence intervals. Frequency distributions will also be calculated for each combination of technique and evaluation category, along with 95% confidence intervals. SPSS (Version 22) and R (Version 3.1.2) will be used in the analysis.

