The Principal Investigator will determine whether subjects (either withdrawn subjects or subjects completing the study) are in need of additional treatment and/or follow-up observation as a result of participation in this trial (such as if a restoration fails). Additional treatment may be needed for teeth that are not included in this study, but require a restoration. Subjects and/or their insurance will be responsible for the cost of any standard of care follow-up visits or additional treatment that is not part of this study.

- E) Assessment
  - 1) Risk

The patient may expect the usual post-operative pain or sensitivity that is typically associated with the standard of care placement of dental restorations, (the risks for both groups is anticipated to be the same and are not greater than standard of care risks), including: tooth pain, bite pain/sensitivity, gingival sensitivity/tenderness/redness, discomfort from the anesthetic, or allergic reaction to the anesthetic. These events are expected to be *localized* and *transient in nature*.

Another potential risk is partial loss, chipping, or fracture of the restoration, trauma to restored or adjacent teeth, or total loss of the restoration. However, the rate of occurrence is anticipated to be very low (no higher than for other restorations).

The risk of radiographs will be kept to a minimum using standard of care procedures (lead apron, digital radiographs, etc.). It is standard of care to have bitewing radiographs annually for caries detection. It is standard of care to have periapical radiographs prior to class II restorations to ensure there are no signs of periapical pathology. These risks are not beyond standard of care risks. At radiograph time, all female subjects will be questioned regarding pregnancy. Any responding positively at the time of screening will be excluded in accordance with the inclusion/exclusion criteria. If a subject becomes pregnant during the course of the study, radiographs will be delayed until after delivery.

There is the risk of loss of confidentiality to the subject by participating in this study. This risk will be kept to a minimum by following procedures listed under confidentiality section.

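### Does the 16.6% margin of error commit the trial to normal-approximation intervals that fail at low percentages?

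*Combined protocol and SAP*

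**What the plan says.** The Sample size section (III.B) rests on precision alone. It states that "A sample size calculation was conducted using nQuery Advisor (version 7.0") and that, "with a sample size of n=35 subjects", "all 95% confidence intervals will have a margin of error of no more than 16.6" percent. It then adds an allowance for attrition: "Up to 44 subjects will be treated to allow for 20% dropout". It gives no assumed proportion and no formula.

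The Statistical analysis section says that since comparable results "are anticipated, confidence intervals will be used rather than p-values". In each category it plans percentages for SonicFill 2 better, Filtek Supreme Ultra better and the two equal; for the last of these, "the percentage of times with equal performance will be calculated along with 95% confidence intervals". It also says: "Frequency distributions will also be calculated for each combination of technique and evaluation category, along with 95% confidence intervals". SPSS and R are named as software, but no interval method or function is given.

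The only statement about expected event rates is in the Risk section (III.E.1). On loss, chipping or fracture of a restoration and trauma to teeth, it says that "the rate of occurrence is anticipated to be very low". No numerical rate appears anywhere.

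**The concern.** The precision statement is the only justification for the sample size, and confidence intervals are the only inferential tool. The figure of 16.6% matches the Wald half-width at 50%, so a reader could suppose that Wald intervals will also be used in the analysis.

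That would be a poor choice for some of the planned percentages. Appendix A has five grades per category, and grades 4 and 5 may well be empty or nearly so for both materials. A Wald interval on 0/35 has zero width, so it would seem to rule out unacceptable restorations when the data still allow a rate near 10%. If the analyst turned to exact intervals to avoid this, the promise about all intervals would no longer be literally true. On that reading, the plan must give up either its 95% coverage or its 16.6% bound.

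**Working it through.** **Inputs.** n = 35, 95% confidence and the bound of 16.6% come from the Sample size section. Two-sided intervals are assumed, since sidedness is not stated. The true rates used for coverage are assumptions, because the documents give none.

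**1. The plan's figures.** The Wald half-width is z√(p(1−p)/n), which is largest at p = 0.5:

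1.96 × √(0.25/35) = 0.1656, or 16.6%.

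In reverse, 1.96² × 0.25/0.166² = 34.85, which rounds up to 35. The attrition figure also reproduces: 35/0.8 = 43.75, so 44. There is no arithmetic error.

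**2. Wald at low counts.**

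- 0/35: 0% to 0%
- 1/35: −2.7% to 8.4%
- 2/35: −2.0% to 13.4%
- 3/35: −0.7% to 17.9%

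Coverage is the sum of binomial probabilities over the counts whose interval contains the true rate:

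| Assumed true rate | Wald | Wilson | Exact |
|---|---|---|---|
| 1% | 29.7% | 95.2% | 99.5% |
| 2% | 50.6% | 96.8% | 99.5% |
| 3% | 65.5% | 98.0% | 98.0% |
| 5% | 83.2% | 97.1% | 99.3% |
| 8% | 94.0% | 94.3% | 98.1% |
| 10% | 87.1% | 92.0% | 98.0% |
| 50% | 95.9% | 95.9% | 95.9% |

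The fault in Wald is therefore real at rates of about 5% or less and, by symmetry, of about 95% or more.

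**3. Which methods respect the bound.** Every count from 0 to 35 was checked. Half-width is half the interval's length; longest arm is the greater distance from the estimate to a limit.

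| Method | Largest half-width | Longest arm | Within 16.6%? |
|---|---|---|---|
| Wald | 16.56% | 16.56% | Yes |
| Wilson, no continuity correction | 15.7% | 16.56% | Yes |
| Jeffreys | 16.0% | 16.5% | Yes |
| Exact (Clopper-Pearson) | 17.3% | 17.9% | No |
| Wilson, continuity-corrected | 17.0% | 18.0% | No |

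**4. Where exact intervals exceed it.** The half-width passes 16.6% only for 13 to 22 of 35 (37% to 63%), by at most 17.3 − 16.6 = 0.7 points. The longest arm passes it for 7 to 28 of 35 (20% to 80%), by at most 17.9 − 16.6 = 1.3 points. At low counts the exact interval stays inside: 0/35 gives 0% to 10.0%, and 6/35 gives 6.6% to 33.7% (half-width 13.5%, longest arm 16.5%). So the range where Wald breaks down is not the range where exact intervals exceed the bound.

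**5. Effect of the number evaluated.** With all 44 treated subjects evaluable, the exact maxima are 15.4% (half-width) and 15.9% (longest arm), both inside the bound. By half-width, 39 subjects are enough (16.4%).

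**The case for a change.** The best argument for a change is that the interval method is open exactly where this trial does its inference. Among the methods tried, only plain Wald gives 16.6% as its largest half-width, so a literal reader may be led to it. Empty or near-empty cells are foreseeable for grades 4 and 5, and a zero-width interval on such a cell would mislead. Naming a method takes one sentence and no extra subjects.

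Some of this stands. Wald would be a bad choice for rare grades, the word all is literally false for exact intervals at n = 35, and a named method would be tidier.

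The rest is weaker. A worst-case normal approximation is a conventional planning device and does not bind the analysis. Support for low percentages is thin: the Risk statement covers loss, chipping, fracture and trauma, not luster, staining or color match. Comparable results need not mean few differing pairs either, since 25% better, 50% equal and 25% worse would also be comparable. Nor is there one flawless method to prescribe: Wilson coverage at n = 35 falls to 83.9% at an assumed rate of 0.5% and 89.8% at 1.55%.

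**Conclusion.** No change is needed. The 16.6% is correctly calculated, and the supposed choice between 95% coverage and the stated bound does not arise, because Wilson and Jeffreys intervals meet the bound at every count. An analyst who prefers exact intervals would exceed it by at most 0.7 points in half-width or 1.3 in the longest arm, and only for mid-range percentages. No comparability margin, success threshold or test depends on the figure, so an excess of that size alters no conclusion.

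What remains is an unnamed interval method, which an analyst can settle sensibly under the plan as it stands. This rests on two-sided intervals, 35 evaluable pairs and an analyst who does not report a zero-width interval for an empty cell. The coverage figures depend on assumed true rates; the bounds on interval width do not.

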#### Statistical analysis

Tables of descriptive statistics (counts and percentages for categorical variables, means and standard deviations for continuous variables) will be prepared to summarize the demographic characteristics of the patients, the distribution of restorations and baseline data, and to illustrate the recall and data analysis findings. Because the hypothesis of the study does not involve superiority of one technique over another, and comparable results between SonicFill™ 2 and Filtek™ Supreme Ultra are anticipated, confidence intervals will be used rather than p-values. In particular, for each evaluation category, the percentage of times that SonicFill™ 2 outperforms Filtek™ Supreme Ultra, the percentage of times that Filtek™ Supreme Ultra outperform SonicFill™ 2, and the percentage of times with equal performance will be calculated along with 95% confidence intervals. Frequency distributions will also be calculated for each combination of technique and evaluation category, along with 95% confidence intervals. SPSS (Version 22) and R (Version 3.1.2) will be used in the analysis.

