#### 2) Exclusion Criteria

Subjects will be considered ineligible for the study if they meet any criterion listed below:

- Is currently taking part in an evaluation of other dental restorative materials
- Has chronic periodontitis or rampant caries
- Teeth exhibiting clinical signs of periapical pathology
- Teeth with a history of self-reported preoperative pulpal problems
- Women who are pregnant (self-reported). It is standard of care to postpone routine dental procedures and radiographed until after pregnancy.
- Women who are breast feeding.
- Known allergy to resin composites or local anesthetics.
- An employee of the sponsor or members of their immediate family.
- Condition affecting salivary flow (e.g., salivary gland disorder, Sjögren's Syndrome)
- Any restorative treatment of the teeth involved in the study in the last 12 months.
- Are unwilling or unable to have dental radiographs or photographs taken of their dentition and soft tissues

- Any other condition which is the view of the investigator may affect the ability of a patient to complete the study.
- 3) Subject Withdrawal/Termination Criteria
  - Subjects who do not comply with the study procedures, such as returning for follow up visits may be withdrawn from the study.
  - Subjects who decide to stop participating in the study will be withdrawn.
  - Subjects who have a clinical pulp exposure during restoration visit will be withdrawn from study and standard of care procedures for pulp exposure and restoration placement will be followed and patient will be advised if they need further treatment and should be seen by a dentist outside the study (such as root canal therapy and/or crown).
  - Subjects who have external procedures or treatments performed on study teeth will be withdrawn from the study. However, if external treatment is only performed on one study tooth, the subject can still participate in the study and the remaining, unaffected study tooth will still be monitored for research purposes.
  - Unanticipated Adverse Device Effect

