If after going through the consent form, the participant indicates s/he would like to discuss the study with associates or think about participating, then the meeting will be ended and the participant will be asked to contact the study when s/he makes her decision. If the participant contacts the study in the future for participation, s/he will be invited back to the clinic, and if informed consent is given at that time, study activities will begin then.

If the participant indicates s/he may be interested in participating after going through the consent form with the investigator, and the investigator determines the participant has the capacity to provide informed consent, the participant will be asked to provide informed consent at that time. Patients will certify their willingness to participate in the study by signing and dating the IRB approved informed consent document. The subject will be given a copy of the consent form.

If any new finding requires any change to the informed consent form, the subject will be re-consented.

Non-English speaking subjects will not be enrolled in the study because study staff at this time are not certified, prepared, or trained to translate or communicate in any language other than English. The study budget does not allow for the payment of translation services at this time. There are no direct benefits to this population by participating in this study.

3) Study Location

Tufts University School of Dental Medicine

Clinical Evaluation of Kerr SonicFillTM 2 vs 3M ESPE FiltekTM Supreme Ultra Universal Restorative PI: [name], DMD, MS, PhD

4) Personnel

Ongoing communication with the IRB and sponsor – The PI Obtaining consent – The PI or his representative Conducting screenings – The PI or Co-Is Placement of restorations – The PI or Co-Is Evaluation of restorations – The PI or Co-Is (who did not place restoration) Maintaining paperwork – The PI and/or study coordinator

- 5) Anticipated Study Timeline\*
  - Protocol and ICF Submission to the IRB: September 2016
  - Approval by the IRB: October 2016
  - Subject Recruitment, Screening, Enrollment and Randomization: June 2017-December 2017
  - Placement of Restorations- June 2017-January 2018
  - Initial Report- January 2018-February 2018
  - Six Months Follow up- December 2017- June 2018
  - Six Months Report- July 2018-August 2018
  - One year follow up- June 2018-December 2018
  - One year Report- January 2019- February 2019

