  - Two year follow up- June 2019-December 2019
  - Final Clinical Study Report- December 2019- January 2020

\*this timeline is subject to change depending on completion of study enrollment

- 6) Payment for Participation
  - (a) Compensation

Restorations will be provided free of charge. A total stipend of up to \$245 in gift-card form will be awarded per subject in the manner as follows: \$25 at screening; \$50 at baseline; \$50 at six month recall; \$50 at one year; and \$70 at two years. Gift cards to Target will be given. The subject will not receive compensation for any missed recall appointments. Subjects will be responsible for paying all procedural costs not study related, as well as costs incurred after the study expires.

(b) Transportation

No travel reimbursement or transportation costs will be paid. Expenses, such as parking and transportation costs, will be paid by the subject at all times.

(c) Payment and Insurance Neither the subject, nor their insurance company, will be billed for any study procedures.

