#### K) Reporting

Progress reports on the investigation shall be submitted to the sponsor and the IRB at regular intervals, but in no event less often than yearly. Progress reports to the sponsor should follow baseline, 6 month, 1 year, and 2 year evaluations. A final study report shall be submitted to the sponsor and IRB following termination or completion of the study. Study completion will be defined as completing assessments on the last subject and presentation of final report

Unanticipated problems and adverse events will be reported per the Tufts MC/TUHS IRB Reportable New Information Policy.

The IRB will be notified of any deviations from the protocol in cases of medical emergencies when the change is necessary to eliminate an apparent immediate hazard to the subject

Progress reports on the investigation shall be submitted to the IRB at regular intervals, but in no event less often than yearly, e.g., at continuing review.

L) Protocol Deviations

No protocol changes or deviations will be made without prior agreement by the IRB and the study sponsor unless implemented to prevent an immediate hazard to subjects. All other protocol changes or deviations will be made by a formal amendment subject to IRB approval and with sponsor agreement. All such changes or deviations will be reported to the IRB as they occur and included in the final study report.

M) Study Termination

This study may be terminated for the following reasons:

Discovery of unforeseen risk that could jeopardize the dental/physical well-being of subjects.

Enrollment or recall rates that are not likely to produce sufficient data for evaluation of safety and efficacy

Non-compliance with the clinical investigational plan, the Investigator Agreement, applicable FDA regulations or conditions of approval imposed by the reviewing IRB

Withdrawal of IRB approval

Any other reasons allowed by study agreements/contracts between the sponsor and the institution.

In the event of study termination, the Principal Investigator will determine whether subjects are in need of additional treatment and/or follow-up observation as a result of participation in this trial.

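### Overall clinical acceptability is part of the comparability hypothesis but is never defined or analysed, and the plan gives no paired-difference interval and no criterion for calling the materials comparable

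*Combined protocol and SAP*

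**What the plan says.** The hypothesis, at the end of section I.A (Aim/Hypothesis/Objective), is that SonicFill 2 will be comparable to Filtek Supreme Ultra "in overall clinical acceptability and in all compared categories". It is presented as a hypothesis to be tested.

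Section III.B, Statistical analysis, chooses intervals over p-values: "Because the hypothesis of the study does not involve superiority of one technique over another". For each category it plans the percentages of pairs in which each material does better, and "the percentage of times with equal performance will be calculated along with 95% confidence intervals". It adds grade distributions for each material and category, also with 95% intervals. It names no main time point.

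Section III.B, Sample size, states that with 35 subjects "all 95% confidence intervals will have a margin of error of no more than 16.6" percent, and allows up to 44 treated for 20% dropout.

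Section III.D.3 (Subject Withdrawal/Termination Criteria) says that if only one study tooth is treated outside the study, "the remaining, unaffected study tooth will still be monitored for research purposes". Appendix A grades each category from 1 to 5. Grade 4 is labelled unsatisfactory and grade 5 poor.

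**The concern.** The design is split-mouth, so the natural answer to a comparability question is a within-patient difference with its interval, read against something stated in advance. Four elements are missing.

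- **Overall acceptability.** The term appears once, in the hypothesis. No cut-off, worst-category rule or composite turns the category grades into one result per tooth.
- **A paired interval.** Win, loss and tie percentages each get their own interval. The difference between materials gets none.
- **A criterion.** Nothing says whether comparable means one-sided non-inferiority or two-sided equivalence, or how close is close enough.
- **Broken pairs.** No section says how a pair is analysed once one tooth has left. If the tooth left because its restoration failed, omitting the pair removes the failure from the comparison.

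At stake is whether the final report can answer the stated hypothesis, or whether comparable will be defined after the results are known.

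**Working it through.** **1. The plan's own figure.** Inputs: n = 35, 95% confidence, and the worst case p = 0.5 for a single percentage. Half-width = 1.96 × √(0.25/35) = 0.166, or 16.6%. Dropout: 35/0.8 = 43.75, so 44. Both reproduce.

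**2. Can overall acceptability be recovered from the planned tables?** Appendix A shows 13 category columns. Suppose each shows 1 of 35 restorations of one material unacceptable. If it is the same tooth each time, the overall rate is 1/35 = 2.9%. If it is a different tooth each time, the rate is 13/35 = 37.1%. These are arithmetic extremes, not forecasts, but they show that per-category tables do not fix the overall rate.

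**3. Can the per-category difference be recovered?** Yes. For example, 2 wins and 2 losses in 35 pairs are 5.7% each. The paired difference is 0, with a Tango 95% interval of -14.1 to +14.1 points. The counts suffice, but the plan does not ask for the interval.

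**4. Precision of the paired difference.** Let b and c be the pairs favouring SonicFill and Filtek. The Tango limits are the values of Δ that solve

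(b - c - nΔ) / √(n[2q + Δ(1 - Δ)]) = ±1.96,

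where q = (√(B² - 4AC) - B)/(2A), A = 2n, B = -b - c + (2n - b + c)Δ, and C = -cΔ(1 - Δ).

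With no discordant pairs this reduces to 1.96²/(35 + 1.96²) = 3.84/38.84 = 9.9 points. The documents give no discordance rate, so a range is assumed, with b = c:

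| Discordant pairs | Tango half-width (points) | Simple 1.96 × √(d/35) |
|---|---|---|
| 0% | 9.9 | 0 |
| 10% | 13.7 | 10.5 |
| 20% | 16.6 | 14.8 |
| 25% | 17.9 | 16.6 |
| 50% | 23.3 | 23.4 |

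The simple formula is too narrow at low discordance, which is where a binary acceptability endpoint is likely to lie.

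**5. What a margin would mean with 35 pairs.** Assumptions: truly equal materials, failures independent within a patient, and unacceptable share f for each. Each discordant cell is f(1 - f), so total discordance is 2 × 0.05 × 0.95 = 9.5% at f = 0.05 and 2 × 0.10 × 0.90 = 18% at f = 0.10. Summing over all possible (b, c) gives the chance of meeting an illustrative 20-point margin:

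| Reading | 95% acceptable | 90% acceptable |
|---|---|---|
| One-sided, lower limit of 95% interval | 85% | 71% |
| Two-sided, 95% interval | 70% | 42% |
| Two-sided, 90% interval | 90% | 68% |

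**The case against.** The strongest reply is that this is an estimation study. It is sized for precision, it chooses intervals over tests, and its primary objective is a comparison in listed categories, every one of which is to be analysed. That is a legitimate design and most of the reply stands. No margin is obligatory, the per-category paired interval is a short calculation from the planned counts, and the sample-size arithmetic is sound. The reply does not supply a definition of overall acceptability, and it does not fit a hypothesis described as one to be tested.

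Three stronger readings are tempting.

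- A reader might infer that the 16.6% figure is an error. It is not. It describes single percentages, which are what the plan names.
- A reader might infer from the simple formula that 16.6 points also covers the paired difference up to 25% discordance. With a Tango interval it does so only up to about 20%.
- A reader might infer that broken pairs will reverse the conclusion. Three SonicFill-only failures among 35 pairs give -3/35 = -8.6 points (-22.4 to +2.2). If those pairs are dropped, 32 concordant pairs give 0 (-10.7 to +10.7). A 15-point margin is failed in the first case and met in the second. But this needs three failures all on one side, all treated elsewhere and all omitted, and the documents do not say such pairs are omitted. The Policy Regarding Replacement of Restorations also has an independent dentist evaluate the cause of failure before re-treatment, so some failures would be documented. What stands is that the handling is unspecified.

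**Conclusion.** The point holds as a gap that is cheap to close. As written, the plan cannot answer the overall-acceptability part of its hypothesis. It describes the category part without a paired interval or a rule for reading it. It would go too far to say that the categories are left unanalysed or that the sample size is wrong, because every listed category is summarised and both sample-size figures reproduce.

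The size depends on discordance, which the documents do not give. Over an assumed 0% to 50%, the Tango half-width runs from 9.9 to 23.3 points with 35 pairs. Acceptability rates, independence of failures and the 20-point margin are illustrative assumptions, not proposals.

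Timing leaves room to act. This version is dated 11/2/2018 and the timeline, which is subject to change, gives "Two year follow up- June 2019-December 2019". However, it also gives "Six Months Report- July 2018-August 2018", and section K says "Progress reports to the sponsor should follow baseline, 6 month, 1 year, and 2 year evaluations". The documents do not say whether those reports show results by material, so a margin set now may not be fully blind to interim findings.

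**What to change.** 1. **Overall acceptability as the main comparison.** Define it per tooth from Appendix A, for example all listed categories graded 1-3, and list the categories that count. Check that each of the 14 categories in section I.A has a grading column. None is visible for approximal form and contact point, which may be an artefact of the PDF. Report the paired difference in percent acceptable at 2 years, SonicFill minus Filtek, with a 95% Tango interval. In this analysis, count a restoration that failed or was replaced before 2 years as unacceptable, using the independent failure evaluation where available. State how other broken pairs and missing teeth are handled.
2. **Categories.** Add percent win minus percent loss with a paired 95% interval, labelled supportive.
3. **Meaning of comparable.** Either state non-inferiority or equivalence with a margin for the overall endpoint, justified by the sponsor and fixed before further comparative results are seen, and record any interim results already known. Or reword the hypothesis and conclusions as descriptive estimation.
4. **Sample size section.** State that 16.6% applies to single percentages, and give the Tango half-widths for the paired difference: about 9.9, 13.7, 16.6, 17.9 and 23.3 points at assumed discordance of 0, 10, 20, 25 and 50%.

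The cost is SAP wording, one sponsor decision, a recorded reason when a study tooth is treated elsewhere, and a few lines of R. The grades are already scheduled, so no extra patients or visits are needed. The downside of choosing a margin is limited power, as the last table in the working shows.
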